### 4.3. Removal of Patients from Therapy

Patients have the right to withdraw from the study at any time for any reason. The investigator has the right to withdraw patients from the study according to his/her discretion. When a patient discontinues treatment early, every effort will be made to conduct a post-treatment follow-up visit within 4 weeks after the last dose of study drug or prior to the initiation of new treatment. This post-treatment evaluation may be conducted over the phone if the patient is unable to return to the clinic. The reason(s) for withdrawal must be recorded.

Criteria for terminating participation in the study are listed below:

- Clinically significant progressive disease defined as > 50% increase in the percentage of blasts in bone marrow or peripheral blood over baseline to reach at least 20% blasts in bone marrow or peripheral blood by two assessments while on treatment with an adequate dose
- Lack of efficacy refers to treating physician's judgment that patients are unlikely to benefit from continuation of treatment despite not meeting the criterion of clinically significant progressive disease.
- Unacceptable toxicity
- Patient withdrawal of consent for treatment
- Investigator's discretion that it is in the best interest of the patient to withdraw
- Intercurrent illness: a condition, injury, or disease unrelated to cancer in the opinion of the investigator, that renders continuing sapacitabine treatment unsafe or regular follow-up impossible

- General or specific changes in the patient's condition that renders the patient ineligible for further treatment
- Noncompliance with study medication or protocol-required evaluations and followup visits
- Termination of the clinical trial by the sponsor

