#### 9. EFFICACY ASSESSMENT

The primary efficacy endpoint of Part 1 of this study is 1-year survival, i.e., the proportion of patients who are alive at 1-year measured from the date of the randomization. Secondary efficacy endpoints are the rate of CR, CRp, PR or CRi or hematological improvement and their corresponding durations, transfusion requirements and number of hospitalized days. The primary efficacy endpoints of Part 2 of this study are the rate of clinical benefit response (CR, CRp, PR, or major HI) and the rate of complete response (CR or CRp). Secondary efficacy endpoints are response durations, transfusion requirements, number of hospitalized days, and overall survival. The primary efficacy endpoint of Part 3 and 4 of this study is 1-year survival rate. Secondary efficacy endpoints are the rate of clinical benefit response (CR, CRp, PR, major HI or SD) and their corresponding durations, transfusion requirements, number of hospitalized days and overall survival.

The tissue samples supporting the diagnosis of AML or MDS, and the responses to sapacitabine may be submitted for central review.

Table 6 Response Criteria

Passansa Description					
Response	Description				
Complete Remission (CR) 	Normalization of peripheral neutrophils to ≥1000 /µL, platelet to ≥100,000/µL within 2 weeks of bone marrow biopsy/aspirate, and bone marrow to ≤5 % blasts; independent of transfusions*; and no extramedullary leukemia.				
Complete remission with incomplete platelet count recovery (CRp) 	Normalization of bone marrow to $\leq$ 5% blasts; peripheral neutrophils $\geq$ 1000 /µl, platelet $<$ 100,000 /µL within 2 weeks of bone marrow biopsy/aspirate; independent of transfusions*; and no extramedullary leukemia.				
Complete remission with incomplete blood count recovery (CRi) 8	Normalization of bone marrow to $\leq$ 5% blasts; peripheral neutrophils $<1000~/\mu$ L, platelet $<100,000/\mu$ L within 2 weeks of bone marrow biopsy/aspirate; independent of transfusions *; and no extramedullary leukemia.				
Partial Remission (PR) 8	Normalization of peripheral neutrophils to $\geq 1000 \ / \mu L$ , platelet to $\geq 100,000/\mu L$ within 2 weeks of bone marrow biopsy/aspirate, $\geq 50\%$ decrease in bone marrow blasts over pretreatment but still >5%; independent of transfusions * .				
Hematological improvement (HI) 9	Major response:				

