	(1) For patients with pretreatment hemoglobin < 11 g/dL, >2g/dL increase in hemoglobin; for RBC transfusion - dependent patients, transfusion - independence*				
	(2) For patients with a pretreatment platelet count <100,000/mm³, an absolute increase of ≥30,000/mm³; for platelet transfusion-dependent patients, stabilization of platelet counts and platelet transfusion independence*.				
	(3) For patients with absolute neutrophil count (ANC) $< 1,500/$ mm  before therapy, $\ge 100\%$ increase, or an absolute increase $> 500/$ mm  , whichever is greater.				
	Minor response:				
	(1) For patients with pretreatment hemoglobin < 11 g/dL, 1-2 g/dl increase in hemoglobin; for RBC transfusion – dependent patients, 50% decrease in transfusion requirements.				
	(2) Platelet response: for patients with a pretreatment platelet count $<100,000/\text{mm}^3, \ge 50\%$ increase in platelet count with a net increase $>10,000/\text{mm}^3$ but $<30,000/\text{mm}^3$ .				
	(3) For patients with absolute neutrophil count (ANC) $< 1,500/$ mm  before therapy, $\ge 100\%$ increase, but absolute increase $< 500/$ mm  .				
Stable disease (SD)**	Failure to achieve at least HI, but no evidence of clinically significant progression for > 16 weeks.				

\*independent of transfusions or transfusion –dependence refer to no packed red blood cell transfusion for 2 weeks and no platelet transfusion for 1 week .

Transfusion requirements for each patient are defined as the number of weeks during which at least one transfusion for red blood cells (RBCs) or platelets is administered and the mean number of units of RBC and platelet transfusions administered per month.

CYCLACEL LTD CONFIDENTIAL 34 of 56

\*\* for Part 2, 3 and 4 of the study only

Clinical benefit is defined as the achievement of CR, CRp, PR, major HI or SD. The duration of clinical benefit is measured from the earliest time when the patient achieved CR, CRp, PR or major HI to the first date when the major HI is lost; if the patient only achieved SD, the duration of clinical benefit is measured from the date of randomization or registration to the first date when clinically significant progression of disease is observed.

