The duration of CR, CRp, PR or CRi or hematological improvement is measured from the time when response criteria are first met until the first date that recurrent or progressive disease is documented. To avoid premature discontinuation of patients who have had a temporary flare of the disease due to treatment interruptions, dose reductions, acute infection or other plausible explanations, a second assessment should be performed in these patients to confirm the recurrence or progression of disease.

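### The end rule for duration of hematological improvement (HI) does not name loss of the improvement, so HI duration is biased upward, most clearly in Part 1 and for minor HI

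*Combined protocol and SAP*

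**What the plan says.** Section 9 makes HI duration a secondary endpoint of Part 1: "Secondary efficacy endpoints are the rate of CR, CRp, PR or CRi or hematological improvement and their corresponding durations". The last paragraph of that section sets the start for four remission categories and HI together: "The duration of CR, CRp, PR or CRi or hematological improvement is measured from the time when response criteria are first met". It also sets one end for all five, since each duration runs "until the first date that recurrent or progressive disease is documented".

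Table 6 defines HI, major and minor, by changes in hemoglobin, platelets or neutrophils, or by reduced transfusion need. One major criterion, for example, is ">2g/dL increase in hemoglobin". No HI criterion refers to blasts.

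Progression is defined once, in Section 4.3, as a reason for ending participation: "Clinically significant progressive disease defined as > 50% increase in the percentage of blasts in bone marrow or peripheral blood over baseline", reaching at least 20% on two assessments. Recurrent disease is not defined.

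For clinical benefit, Section 9 has a different rule just below Table 6. That duration runs from the earliest "CR, CRp, PR or major HI to the first date when the major HI is lost".

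Section 11.4 lists HI among the durations to be estimated by Kaplan-Meier. It censors patients who leave for reasons other than progression at their last response evaluation. It adds no event for loss of HI.

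**The concern.** The duration of a response should end when the response ends. A remission and blast-based progression are largely measured on the same scale, so the shared rule fits remissions reasonably well. HI is measured on another scale. Counts can return to pretreatment values, or transfusions can resume, without any change in blasts, and the rule then has no stated event to record.

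At stake is what the reported figure means. A median HI duration under this rule reads as how long patients kept their improvement, but it is closer to time to blast progression. A short-lived improvement could be reported as durable. This matters most in previously treated MDS, where Section 11.1 sets the CR-based screening aside and Section 11.1.1 counts major HI among the responses that can justify adding patients.

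**Working it through.** The documents give no assumed value, power or precision for HI duration, so there is no plan figure to reproduce. The check sets the definitions side by side and then illustrates size with assumed times.

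**Step 1: follow one patient through the rules.** Assume HI is lost 8 weeks after onset with stable blasts, and blast progression is documented 16 to 32 weeks after onset.

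- General duration rule (end of Section 9): no stated event at week 8; event at week 16 to 32.
- Clinical benefit rule (below Table 6), if the HI was major: event at week 8.
- Difference: 16 − 8 = 8 weeks to 32 − 8 = 24 weeks, or 16/8 = 2 to 32/8 = 4 times as long.
- If the patient instead stops for lack of efficacy, which Section 4.3 lists separately from progression, Section 11.4 censors at the last response evaluation. The clock stops, but the loss is never an event.

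**Step 2: where the gap applies.**

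- Part 1, AML and MDS strata: HI duration is a named secondary endpoint and clinical benefit is not an endpoint, so only the general rule applies.
- Minor HI: it is outside clinical benefit, so no loss rule exists for it anywhere.
- Parts 3 and 4, major HI: Sections 2 and 9 attach duration to clinical benefit, whose rule already ends at loss of major HI. Sections 11.3 and 11.4 can be read as also wanting durations of the components. If those are reported, the two rules give one patient two different durations.

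**Step 3: direction.** For each patient, time to progression cannot be shorter than the earlier of loss and progression. Ignoring loss therefore lengthens true HI time or leaves it unchanged. Censoring after an unrecorded loss removes the drop in the curve that the loss should have caused.

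**Step 4: size under assumptions.** Let L be the median time to loss and P the median time to blast progression, with independent exponential times. The median time to the first of the two is M = 1/(1/L + 1/P). The present rule targets P, so the overstatement is P/M = 1 + P/L. Assumed ranges, not taken from the documents: L = 2 to 4 months, P = 6 to 12 months.

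| L | P | M (months) | P/M |
|---|---|---|---|
| 4 | 6 | 1/(1/4 + 1/6) = 2.4 | 2.5 |
| 2 | 6 | 1/(1/2 + 1/6) = 1.5 | 4 |
| 4 | 12 | 1/(1/4 + 1/12) = 3.0 | 4 |
| 2 | 12 | 1/(1/2 + 1/12) = 1.7 | 7 |

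If counts fall mainly because the disease advances, loss and progression come close together and the ratio moves towards 1.

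**The case against.** The strongest reply is that the text is ambiguous rather than wrong. Section 4.3 defines clinically significant progression for ending participation, while the duration rule uses the unqualified terms, and recurrence could be read to include loss of HI. The ambiguity is real. However, nothing in the documents gives that reading, and when Section 9 means loss of HI, a few lines earlier, it says so: "to the first date when the major HI is lost". At best, sites and analysts are left to choose.

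A second reply is that censoring limits the damage. It does stop the clock for patients who leave for other reasons. A reader might infer that everyone back at pretreatment counts goes on accruing HI time until progression; Section 11.4 does not support that. The loss still goes uncounted.

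A third reply is that Parts 2 to 4 are already covered. This stands for major HI within clinical benefit, and it narrows the point to Part 1, minor HI and any separate reporting of major HI.

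Finally, HI duration drives no decision. Screening uses response rates (Sections 11.1.1 and 11.3.1), and selection uses 1-year survival without a formal test (Sections 11.1.2 and 11.3.2). This stands, and it limits the importance of the point.

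**Conclusion.** The point holds in a limited form. The stated end event for HI duration does not name loss of the improvement that defines HI, so loss with stable blasts is either passed over until progression or censored. The resulting Kaplan-Meier estimate is biased upward as a measure of how long HI lasts. This rests on reading progression as Section 4.3 defines it, the only definition available, and on recurrence having no stated meaning that covers loss of HI.

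The size cannot be derived from the documents. The range of 2.5 to 7 times depends wholly on the assumed medians and on independence. A single fourfold figure might be inferred, but it arises only when P is three times L.

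Nor does the point reach 1-year survival, the response rates or any stopping or selection rule. It is a correctable definition of a descriptive secondary endpoint.

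**What to change.** In Section 9, give HI its own end rule. Suggested wording: HI duration ends at the earlier of (a) loss of the Table 6 improvement that qualified the patient, confirmed by a second assessment, or (b) recurrent or progressive disease.

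Confirmation matters because Section 1.6 expects generally reversible myelosuppression, and a transient treatment-related drop should not end HI. Section 9 already asks for a second assessment where a temporary flare is plausible.

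Three further changes belong with it:

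- Align the rule with the clinical benefit rule, so that a patient with major HI only has one end date.
- Define recurrent disease.
- State how death is handled, in the same way for all response durations; neither Section 9 nor Section 11.4 names it.

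The cost is small. Table 5 already schedules blood counts and transfusion records on Day 1 of each cycle from cycle 2. Reported HI durations will become shorter, and loss will be dated only to scheduled visits, about four weeks apart or more when a cycle is delayed.

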#### 10. INVESTIGATIONAL DRUG INFORMATION AND PROCUREMENT

### 10.1. Study Drug Identity

Chemical Name:

1-(2-C-cyano-2-deoxy-β-D-arabino-pentafuranosyl)-N-

palmitoylcytosine

Molecular Formula: C26H42N4O5 (MW 490.64)

**Oral Formulation (Cyclacel BL formulation which was previously called Encap formulation):** The drug is supplied as 25 mg, 50 mg and 75 mg strength liquid-filled capsules of a suspension of the crystalline Form B of the active pharmaceutical ingredient in miglyol 812N. Capsules are packaged in high-density polyethylene (HDPE) bottles, snap-on tamper evident low-density polyethylene (LDPE) lids closures.

Table 7 Encap Formulation Capsule (mg/capsule)

Ingredient	25 mg	50 mg	75 mg
Sapacitabine Form B	25 mg	50 mg	75 mg
Miglyol 812N Ph.Eur/GRAS	100 mg	200 mg	300 mg
White gelatin capsule with a gelatin band (comprising gelatin USP/Ph Eur and sterile water for irrigation)	Size 3	Size 2	Size 1
Printed white gelatin capsule (blue ink ring on the capsule body and a blue ink ring and a black ink band on the capsule cap) with a gelatin band (comprising gelatin USP/Ph Eur and sterile water for irrigation)	Not applicable	Size 2	Not applicable

**Preparation:** Gelatin capsules are filled with above components and sealed with a gelatin band under Good Manufacturing Practice (GMP) conditions.

**Storage and Stability**: The capsules should be stored at room temperature (15-25°C) in a closed container, protected from light in a secure, limited-access storage area. The 25, 50 and 75 mg capsules are stable for 5 years.

#### Route of administration: Oral

**Source of Drug:** Sapacitabine is an investigational drug supplied by Cyclacel under Investigational New Drug #53748.

### 10.2. Drug Procurement

FDA regulations require investigators to establish a record of the receipt, use, and disposition of all investigational agents. Investigators may delegate responsibility for drug ordering, storage, accountability, and preparation to their designees. Cyclacel's requirements for procurement, accountability, and disposition of study drug are provided below.

### 10.2.1. Drug Ordering

Sapacitabine should be requested by the Principal Investigator (or his/her authorized designees) at each participating institution. Sapacitabine may not be used outside the scope of this protocol, nor can it be transferred or licensed to any party not participating in the clinical study. Cyclacel policy requires that sapacitabine be shipped directly to the institution where the patient is to be treated. Cyclacel does not permit the transfer of sapacitabine between institutions. The instructions for ordering study drug will be provided in the Operations Manual.

#### 10.2.2. Drug Accountability

A capsule count of the drug will be maintained on the Drug Accountability Record (DAR) which has been approved for use by Cyclacel. All drug received, dispensed, and returned by the patient must be recorded on the DAR.

Patients must be instructed to return the dispensed capsule bottle on Day 1 of each cycle. Capsule count will occur at each visit to assess patient compliance with study drug.

#### 10.2.3. Disposition of Unused Drug

All unused drug, including drug returned by patients, must be retained by study site staff until verified by Cyclacel's representative. After the drug accountability has been verified by Cyclacel's representative, unused drug will be destroyed at study site according to local Institutional guidelines and applicable laws and regulations.

#### 11. BIOSTATISTICAL CONSIDERATIONS

### 11.1. Sample Size for Part 1 of the Study

This study is an open-label, randomized study of 3 dosing schedules of sapacitabine. The primary objective of this study is to evaluate 1-year survival rate of 3 dosing schedules in elderly patients with previously untreated or first relapsed AML or previously treated MDS; the secondary objectives are to assess the number of patients who have achieved a CR, CRp, PR or CRi or hematological improvement and their corresponding durations, transfusion requirements, number of hospitalized days and safety.

The primary efficacy endpoint is 1-year survival measured from the date of randomization. Statistically, the purpose of the trial is to reject the dosing schedules from further study if they were insufficiently active based on the rate of CR plus CRi for AML, and to accept them for further study if they were truly active. This will not apply to the MDS stratum because the CR rate of standard therapy by hypomethylating agents is only 6-9% and there is no effective therapy for those who have been previously treated by hypomethylating agents. For "screening" purpose, a Bayesian continuous futility monitoring rule is used for each dose schedule separately based on the rate of CR plus CRi for AML, and a "selection" design to choose the better dosing schedule based on 1-year survival rate if all 3 dosing schedules are found to have activity based on the rate of CR plus CRi. This randomized phase II trial is not expected to have sufficient power to compare the 3 dosing regimens on the basis of 1-year survival rate.

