### 3.3. Rationale for the Proposed Dosing Schedules

Preliminary pharmacokinetic analyses from two completed phase I studies indicate that sapacitabine and its active metabolite CNDAC have a relatively short half-life (approximately 2 hours) and that CNDAC exposure appears to correlate with the worst NCI-CTC grade of neutropenia experienced during treatment at the MTD. We hypothesize that the 7-day high dose regimen will lead to higher dose delivered per week (1400 mg/week) resulting in better antitumor activity than the 7-day low dose regimen (933 mg/week) but may cause more myelosuppression; the 3-day high dose regimen will have higher dose delivered per week (1600 mg/week) resulting in better anti-tumor activity than the 7-day high dose regimen but will have similar degree of myelosuppression and gastrointestinal toxicity because the consecutive days of dosing are shorter. Preliminary data from the 60 patients in the original cohort of the AML stratum showed that the dosing schedule of 400 mg b.i.d. x 3 days/week x 2 weeks every 3-4 weeks has the highest rate of CR/CRp, i.e., 25%, the longest durations of responses, and a 10% all-cause death rate within the first 30 days after randomization. However, all patients who achieved CRs were dose reduced for myelosuppression. We hypothesize that a 3-day dosing regimen of 300 mg b.i.d. x 3 days/week x 2 weeks every 4 weeks will be equally effective but with less myelosuppression and propose to test this dosing regimen in Part 2 of the study. Exploratory subgroup analyses from AML patients enrolled in Part 1 of the study suggest that the 7-day low dose schedule of 200 mg b.i.d. x 7 days every 3-4 weeks (Arm A) may be more effective for AML preceded by MDS or MPD. Among 7 patients on Arm A who have survived at least 1 year, 4 patients have AML preceded by MDS or MPD. We hypothesize that a 7-day once daily (q.d.) dose regimen and a lower dose of the 3-day dose regimen may be equally effective but with less myelosuppression. We propose to evaluate 300 mg a.d. x 7 days and 300 mg b.i.d.

x 3 days/week x 2 weeks every 4 weeks in patients with newly diagnosed AML preceded by MDS after receiving hypomethylating agents for the preceding MDS (Part 3).

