#### 11.1.1. Screening Design

In the screening phase, a Bayesian continuous futility monitoring rule will be implemented based on the rate of CR plus CRi in each of the 3 arms of the AML stratum, respectively. An arm will be stopped if Prob (CR+CRi > 25% | data) < 0.05. The above stopping rule suggests that, given the data obtained from patients who have already been evaluated in an arm, if there is less than a 5% chance that the rate of CR+CRi is greater than 25% we will terminate the arm. This decision rule generates the following stopping boundaries, assuming a beta(1,1) prior distribution for the response (CR+CRi) rate in each arm. Stop an arm i if [ # of pts with CR or CRi in arm i / # of pts evaluated in arm i ]  $\leq$  0/10, 1/17, where i = 1, 2, or 3. The operating characteristics of this rule are shown in Table 8.

Table 8 Operating Characteristics of Futility Monitoring - Maximum 20 AML Patients

		Sample Size		
Rate of CR or CRi	Probability of stopping	P 25	P 50	P 75
0.05	0.822	10	10	17
0.10	0.54	10	17	20
0.15	0.313	17	20	20
0.20	0.165	20	20	20
0.25	0.082	20	20	20
0.30	0.039	20	20	20

After treating up to 10 evaluable AML patients defined as patients who have completed at least 1 cycle of treatment at each dosing schedule

- If no CR or CRi is observed, declare the treatment insufficiently active and no more AML patient will be treated with this dose regimen
- If at least one CR or CRi is observed, add AML patients to reach a total of 17 patients and
  - o If less than two CR plus CRi are observed, declare the treatment insufficiently active
  - o If at least two CR and CRi are observed, add AML patients to reach a maximum of 20 patients

For both AML and MDS patients, there is an early stopping rule for excessive toxicity. A dosing schedule will be declared to have excessive toxicity and no more patients will be treated with this dose regimen if among the first 10 patients treated with this dose regiment in either the AML or MDS stratum, there are > 2 patients experienced serious adverse events (excluding simple complications associated with myelosuppression such as neutropenic fever without shock or its complications from gram-negative bacteremia, anemia or mucosal bleeding, *e.g.*, epistaxis, due to thrombocytopenia easily controlled by transfusion) that are considered by investigator to be definitely, probably or possibly related to the study drug during the first two treatment cycles.

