#### 11.1.2. Selection Design

Assuming that at least 2 dosing schedules show activity and that their toxicity profile is similar, a selection design will be used to choose the dosing schedule with the better observed 1-year survival rate. If the better dosing schedule has a true 1-year rate of 45% and the worse dosing schedule a true 1-year rate of 30%, the trial has better than 80% probability to choose the correct dosing schedule if 20 patients have been treated with each dosing schedule.

No formal hypothesis testing will be carried out for the 1-year survival rate. Instead, we will estimate the 1-year survival rate for each dosing schedule, along with the 95% confidence interval. Given a total of 20 patients in an arm and assuming a 1-year survival rate of 45%, the half-width of the 95% confidence interval will be 0.22. On the other hand, if assuming a 1-year survival rate of 30%, the half-width of the 95% confidence interval will be 0.20.

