#### 11.3. Sample Size for Part 3 and 4

The primary objective of Part 3 and 4 of the study is to evaluate 1-year survival rate of 3 dosing schedules in elderly patients with previously untreated AML which evolved from MDS after receiving hypomethylating agents for the MDS or older patients with previously treated MDS; the secondary objectives are to assess the number of patients who have achieved a CR, CRp, PR, major HI or SD and their corresponding durations, transfusion requirements, number of hospitalized days and safety.

The primary efficacy endpoint is 1-year survival measured from the date of randomization. Statistically, the purpose of the trial is to reject the dosing schedules from further study if they were insufficiently active based on the rate of clinical benefit response and to accept them for further study if they were truly active. For "screening" purpose, a Bayesian continuous futility monitoring rule is used for each dose schedule separately based on the rate of clinical benefit response, and a "selection" design to choose the better dosing schedule based on 1-year survival rate if all 3 dosing schedules are found to have activity based on the rate of clinical benefit response. This randomized phase II trial is not expected to have sufficient power to compare the 3 dosing regimens on the basis of 1-year survival rate.

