#### 11.3.2. Selection Design

Assuming that at least 2 dosing schedules show activity and that their toxicity profile is similar, a selection design will be used to choose the dosing schedule with the better observed 1-year survival rate. If the better dosing schedule has a true 1-year rate of 45% and the worse dosing schedule a true 1-year rate of 30%, the trial has better than 80% probability to choose the correct dosing schedule if 20 patients have been treated with each dosing schedule.

No formal hypothesis testing will be carried out for the 1-year survival rate. Instead, we will estimate the 1-year survival rate for each dosing schedule, along with the 95% confidence interval. Given a total of 20 patients in an arm and assuming a 1-year survival rate of 45%, the half-width of the 95% confidence interval will be 0.22. On the other hand, if assuming a 1-year survival rate of 30%, the half-width of the 95% confidence interval will be 0.20.

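### Sections 11.1 and 11.3 state the schedule selection for three active schedules, 11.1.2 and 11.3.2 for two or more, and for Part 1 MDS activity is not defined

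*Combined protocol and SAP*

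**What the plan says.** For Part 1, section 11.1 describes a futility screen on CR plus CRi for each schedule. A second step would then "choose the better dosing schedule based on 1-year survival rate if all 3 dosing schedules are found to have activity", with activity judged by that screen. Section 11.3 sets the same condition for Parts 3 and 4, with clinical benefit as the measure: "if all 3 dosing schedules are found to have activity based on the rate of clinical benefit response".

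The subsections that describe the selection itself differ. Section 11.1.2 reads: "Assuming that at least 2 dosing schedules show activity and that their toxicity profile is similar, a selection design will be used". Section 11.3.2 opens in the same way: "Assuming that at least 2 dosing schedules show activity and that their toxicity profile is similar". Both then give a probability above 80% of choosing the right schedule when the true 1-year survival rates are 45% and 30% with 20 patients per schedule. Both also say that 1-year survival will not be formally tested.

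For MDS patients in Part 1, section 11.1 exempts the stratum from the CR plus CRi accept-or-reject rule: "This will not apply to the MDS stratum because the CR rate of standard therapy by hypomethylating agents is only 6-9" percent. Section 11.1.1 accordingly runs the screen "based on the rate of CR plus CRi in each of the 3 arms of the AML stratum, respectively". Section 11.4 analyses efficacy separately in the AML and MDS strata.

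**The concern.** Section 1.5 gives choosing a schedule for further development as a reason for the study. Because 1-year survival is estimated and not tested, the selection rule is the only place where the primary endpoint of Parts 1, 3 and 4 leads to a decision. Two entry conditions for that rule, with no order of precedence, mean that the same data can yield a selected schedule or none.

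The study is open label, and section 3.3 already cites Part 1 results by arm, including 1-year survivors on Arm A. A condition left open can therefore be settled after the results are known. In Part 1 about 60 MDS patients are randomized across three schedules, and the plan does not say what would count as activity for a selection among them.

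**Working it through.** **1. Where the texts part.** Outcome by number of schedules that pass the screen:

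| Schedules passing | Toxicity | 11.1 / 11.3 | 11.1.2 / 11.3.2 |
|---|---|---|---|
| 3 | similar | select | select |
| 3 | not similar | select | condition not met |
| 2 | similar | condition not met | select |
| 2 | not similar | condition not met | condition not met |
| 0 or 1 | either | no selection | no selection |

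The second row arises because only 11.1.2 and 11.3.2 carry the toxicity condition.

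**2. Reproducing the stopping probabilities.** Inputs from 11.1.1 and 11.3.1: beta(1,1) prior; stop an arm if the posterior probability of a rate above 25% is below 0.05. This gives the stated boundaries, 0/10 and 1/17. The probability of stopping at true rate p is

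s = P(0 of 10) + P(1 of 10) × P(0 of the next 7).

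At p = 25%: 0.0563 + 0.1877 × 0.1335 = 0.0814, against 0.082 in Tables 8 and 9. Over the six tabulated rates the exact values are 0.819, 0.534, 0.308, 0.164, 0.081 and 0.038, against the stated 0.822, 0.54, 0.313, 0.165, 0.082 and 0.039. The tables hold.

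**3. How often exactly two schedules pass.** Assume three independent arms at the same true rate. Then P(exactly 2 pass) = 3s(1 − s)² and P(all 3 pass) = (1 − s)³.

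| True rate | s (exact) | All 3 pass | Exactly 2 pass | At least 2 pass |
|---|---|---|---|---|
| 30% | 0.0382 | 0.890 | 0.106 | 0.996 |
| 25% | 0.0814 | 0.775 | 0.206 | 0.981 |
| 20% | 0.1637 | 0.585 | 0.343 | 0.928 |
| 15% | 0.3083 | 0.331 | 0.443 | 0.774 |

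The plan's rounded s values give 0.108, 0.207, 0.345 and 0.443 for exactly two. With unequal arms the figure can be larger. For two arms at 25% and one at 10% (s = 0.534) it is 0.9186² × 0.534 + 2 × 0.9186 × 0.0814 × 0.466 = 0.520.

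**4. Part 1 MDS.** Section 11.1 removes the CR plus CRi rule and 11.1.1 screens AML arms only. The one MDS response threshold in 11.1.1 (at least 4 CR, CRp, PR and major HI) permits extra patients to be added; it does not define activity for the selection. Part 4 MDS does not have this gap, because 11.3.1 gives it a clinical benefit screen.

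**5. Probability of correct selection.** Inputs from 11.1.2 and 11.3.2: 45% against 30%, 20 per schedule. Comparing two independent binomial counts:

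- Two schedules: strict win 0.7965, tie 0.0798. With ties split, 0.7965 + 0.0798/2 = 0.836.
- Normal approximation: 0.15 / √((0.45 × 0.55 + 0.30 × 0.70)/20) = 0.15/0.1512 = 0.992, which gives 0.839.
- Three schedules at 45/30/30%: strict win 0.685, plus 0.054 from ties split = 0.740.

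The stated figure therefore describes a choice between two schedules. It does not fit the condition that all three are active.

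**The case against.** The best defence is that 11.1 and 11.3 are overviews and that the subsections headed Selection Design are the operative text. The overviews do not say that selection happens *only* if all three are active, so a reader who infers that is adding a word; the two-or-more condition formally includes the three-schedule case. The stated probability, which fits two schedules, points the same way. This stands as a reason to align the text towards 11.1.2 and 11.3.2. It does not remove the conflict, because no precedence is stated and each overview names its own screening measure.

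The exposure of Part 1 AML is also probably small. Section 3.3 refers to 60 patients in the original AML cohort. With 1:1:1 randomization and a maximum of 20 per arm, 3 × 20 = 60 suggests that all three arms filled and none stopped for futility. Arm counts are not printed, so this is an inference.

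Two stronger readings are tempting. First, a reader might infer that the Part 1 MDS condition can never be met. The documents show only that it is undefined: 11.1 waives one measure, and 11.1.2 asks for activity without naming any.

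Second, a reader might infer that the toxicity condition is bound to fail, since section 3.3 supposes that "a lower dose of the 3-day dose regimen may be equally effective but with less myelosuppression". That does not follow. The natural comparator there is the 400 mg 3-day regimen, which is not a Part 3 arm. For Part 1, section 3.3 expects Arms B and C to have similar myelosuppression and gastrointestinal toxicity. And less myelosuppression is a hypothesis that need not make whole profiles dissimilar. Nor is replacing the condition by the excessive-toxicity rule a correction: that rule leaves out simple complications of myelosuppression, so the swap would be a debatable trade-off.

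**Conclusion.** The concern holds as an unresolved inconsistency between two pairs of sections, with an undefined condition in one stratum. When exactly two schedules pass and toxicity is similar, the texts give opposite outcomes: about 11%, 21%, 34% or 44% of trials at equal true response rates of 30%, 25%, 20% or 15%. These figures assume independent arms and are scenarios, not bounds. They are also not a total disagreement rate, because they leave out the case of three active schedules with dissimilar toxicity. They matter mainly for Parts 3 and 4.

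The correct-selection figure is right for two schedules, with ties split at random or by the normal approximation, and too high for three at 45/30/30%. The per-arm survival estimates and their confidence intervals are unaffected, and no test or error rate for 1-year survival is involved.

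**What to change.** - Align 11.1 and 11.3 with 11.1.2 and 11.3.2: the selection is made among the schedules not stopped by the screen, provided at least two remain.
- For Part 1 MDS, state that the activity condition is waived and that the selection is made among the schedules not stopped under the plan's existing rules.
- Keep the similar-toxicity condition, and reconcile the four sections so that all carry it.
- Restate the probability of correct selection as about 84% for two schedules (45/30%) and about 74% for three (45/30/30%), each with 20 per schedule and ties split.
- Date the clarification and disclose that Part 1 data had been seen when it was made.

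The cost is amendment wording only. No patients, visits or procedures change.
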